#### 9.4.3 Survival Definitions

- OS will be defined by the time interval between the first day of therapy to the time of death or last follow-up, whichever comes first.
- PFS will be defined by the time interval between the first day of therapy to the time of documentation of progression, death of any cause, or last follow-up, whichever comes first.
- DOR will be defined by the time interval between the first documentation of response to the time of documentation of progression, death of any cause, or last follow-up, whichever comes first.
- 

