### 2.3 Rationale

As shown in the study schema the proposed study is a 4-arm Phase 2, open-label study of PARP inhibition (olaparib) in advanced relapsed or refractory *IDH1/2*-mutant AML and MDS. At present, an IDH2 and IDH1 inhibitor, enasidenib and ivosidenib respectively, are FDA approved for the management of patients with IDH2 mutant leukemia (Stein *et al.*, 2015; DiNardo *et al.*, 2018). Based on the scientific rationale described (synthetic lethality of the mutant clone due to accumulation of toxic metabolites), we hypothesize that inhibition of mutant IDH1/2 with small molecule inhibitors is not the most efficacious approach to treat IDH mutant leukemia. Indeed, the synthetic lethality of olaparib is likely most robust in the setting of IDH mutant activity (due to oncometabolite accumulation), and possibly blunted to some degree with the use of an IDH inhibitor. Therefore, we propose a separate arm for evaluation of patients pretreated with IDH inhibitor therapy. In addition, we propose the inclusion of IDH inhibitor-naïve AML patients who present within a "window of opportunity" in this trial (IDH inhibitors are yet to be approved in the MDS setting. AML and MDS have been separated as they are distinct diagnoses, and within each disease group patients have been separated by their exposure to IDH inhibitors; IDH inhibitor naïve and IDH inhibitor exposed. Recognizing that other FDA approved therapeutic options are available, but also that these patients may have a dramatic response to olaparib monotherapy, IDH inhibitor naïve patients will be monitored very closely, including frequent bloodwork and bone marrow evaluation 4 week (or earlier as needed) to safeguard against progression and allow for transition to standard of care therapy within the 12-week period prior to response assessment in the case of progression.

Relapsed/ refractory patients may also have co-occurring targetable mutations, such as FLT3 ITD. At the present time there is no consensus in the AML community on the ideal sequencing of targeted therapies when multiple options are applicable. This is reflected in the current NCCN AML recommendations. In these situations, we will need to rely on the judgement of the local

investigator/ provider to choose the optimal therapeutic option.

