### 6.3 Duration of Therapy

In the absence of treatment delays due to AE(s), treatment may continue until one of the following criteria applies:

- Disease progression
- Intercurrent illness that prevents further administration of treatment
- Unacceptable AE(s)
- Patient decides to withdraw from the study
- General or specific changes in the patient's condition render the patient unacceptable for further treatment in the judgment of the investigator
- Clinical progression
- In patients without prior exposure to IDH inhibitors: the absence of CR/CRh/mCR
- Patient non-compliance
- Pregnancy
  - All women of child-bearing potential should be instructed to contact the investigator immediately if they suspect they might be pregnant (*e.g.*, missed or late menstrual period) at any time during study participation.
  - The investigator must immediately notify CTEP in the event of a confirmed pregnancy in a patient participating in the study.
- Termination of the study by sponsor
- The drug manufacturer can no longer provide the study agent

The reason(s) for protocol therapy discontinuation, the reason(s) for study removal, and the corresponding dates must be documented in the Case Report Form (CRF).

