### 6.4 Duration of Follow-Up

Patients will be seen 90 days after the last dose of the study drug for a follow-up visit and then followed for survival q3 months (+/- 4 weeks) thereafter until death. Patients removed from study for unacceptable AE(s) will be

followed until resolution or stabilization of the AE. Survival data will be followed until death from any cause.

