#### 9.4.2 Evaluation of Objective Response Rate

The effectiveness of the drug in patients for each cohort will be independently assessed by composite CR rate (CR+CRi+CRh). Objective Response Rate (ORR) will be included as a secondary endpoint, calculated as a composite CR+MLFS+PR. The exact two-sided 95% confidence intervals for the ORR will be reported. For lifetime data analyses, e.g., overall and progression free survival, the study survival will be estimated using the Kaplan-Meier method with the 95% confidence intervals (CIs). The CI based on the Greenwoods variance will be reported. In addition, the possible risk factors will be compared for survival with log-rank test. For multivariate analysis, the proportional hazards Cox model will be applied to investigate potential prognostic factors, such as age and stage of disease on the survival data. The adjusted p-values of the odds ratios and the adjusted 95% confidence interval will be reported.

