Progressive disease (PD)	Evidence for an increase in bone marrow blast percentage and/or increase of absolute blast counts in the blood: 
 
• >50% increase in marrow blasts over baseline (a minimum 15% point increase is required in cases with <30% blasts at baseline; or persistent marrow blast percentage of >70% over at least 3 months; without at least a 100% improvement in ANC to an absolute level (<math>>0.5 \times 10^9/L</math> [500/mcL], and/or platelet count to <math>>50 \times 10^9/L</math> [50,000/mcL] nontransfused)
 
• >50% increase in peripheral blasts (WBC <math>\times</math> % blasts) to <math>>25 \times 10^9/L</math> (<math>>25,000/mcL</math>) (in the absence of differentiation syndrome**)
 
• New extramedullary disease
 
	In general, at least two cycles should be administered prior to PD assessment.  Patients with PD may remain on study, after discussion with the PI, if it is judged that they are deriving clinical benefit from doing so.
Primary refractory disease	No CR or CRi after two courses of intensive induction treatment; excluding patients with death in aplasia or death due to indeterminate cause	
Death in aplasia	Death occurring $\geq 7$ days following completion of initial treatment while cytopenic; with aplastic or hypoplastic bone marrow obtained within 7 days of death, without evidence of persistence leukemia	
Death due to indeterminate cause	Deaths occurring before completion of therapy, or $< 7$ days following its completion; or deaths occurring $\geq 7$ days following completion of initial therapy with no blasts in the blood, but no bone marrow examination available	
Hematologic relapse (after CR, CRi)	Bone marrow blasts $\geq 5\%$ ; or reappearance of blasts in the blood; or development of extramedullary disease	
* CBC values for up to 14 days after bone marrow assessment may be used to determine response. ** Certain targeted therapies, e.g. , those inhibiting mutant IDH proteins, may cause a differentiation syndrome, i.e. , a transient increase in the percentage of bone marrow blasts and an absolute increase in blood blasts. In the setting of therapy with such compounds, an increase in blasts may not necessarily indicate PD. ANC=absolute neutrophil count, IDH=isocitrate dehydrogenase, MFC=multiparameter flow cytometry, RT-qPCR=real-time quantitative polymerase chain reaction, WBC=white blood count. (Döhner et al. , 2017)		

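### PFS and DOR run to last follow-up although no disease assessment is scheduled after the 90-day visit, and relapse after CR is not named as an event

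*Combined protocol and SAP*

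**What the plan says.** Section 9.4.3 ends PFS (from first day of therapy) and DOR (from first documented response) at the same point: "to the time of documentation of progression, death of any cause, or last follow-up, whichever comes first". OS uses the same last-follow-up term. Section 9.4.2 adds Kaplan-Meier estimation with Greenwood intervals. Neither section gives a rule for the last disease assessment, new therapy or transplant.

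Section 12.1 schedules response assessment after cycles 3, 6, 9 and 12, plus cycle 1 for patients without prior IDH inhibitor exposure. In the Section 11 calendar both response rows are blank at EOT and at the 90-day visit. A marrow aspiration is marked at EOT. A physical examination and a CBC with differential are marked at 90 days, without a marrow.

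On later follow-up, Section 6.4 says: "Patients will be seen 90 days after the last dose of the study drug for a follow-up visit and then followed for survival q3 months", and "Survival data will be followed until death from any cause".

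Section 6.3 lists several reasons to stop that are not progression: adverse events, intercurrent illness, withdrawal, non-compliance, and "In patients without prior exposure to IDH inhibitors: the absence of CR/CRh/mCR". It gives no time point for the last of these.

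Section 12.1 defines progressive disease (PD) mainly by a rise over baseline blasts. It defines hematologic relapse after CR or CRi in a separate row, starting at 5% marrow blasts.

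**The concern.** There are two problems, and both act in the same direction.

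**Unobserved time.** A patient who stops without documented progression contributes time during which nobody is scheduled to look for progression. Under 9.4.3 that time is progression-free until death or the last survival contact, including any time on another treatment. PFS becomes a mixture of PFS and OS. DOR is affected in responders who stop for toxicity, withdrawal or similar reasons. The stop for lack of response applies to the two IDH-inhibitor-naive arms, each planned at 39 patients, so stopping without PD is foreseen rather than exceptional.

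**Relapse.** For a patient in CR, the event of interest is relapse. If only PD ends DOR, a relapse that stays below the baseline-referenced thresholds leaves the patient counted as still in response.

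At stake is the interpretation of two secondary endpoints in single-arm cohorts, where PFS and DOR would be set beside figures from other studies.

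**Working it through.** The documents state no PFS or DOR target, event count or median, so there is no figure to reproduce. The relapse point needs only the text. The size of the follow-up bias needs assumed inputs.

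**1. Relapse against PD (Section 12.1).**
- Relapse: marrow blasts of at least 5%, blasts reappearing in blood, or extramedullary disease.
- Marrow PD: more than a 50% increase over baseline (at least 15 points if baseline is below 30%), or blasts persistently above 70% for at least 3 months, in either case without the specified count improvement.
- Baseline 60%, CR, relapse to 60%: the increase criterion needs more than 1.5 × 60 = 90%, and the persistence criterion needs more than 70%. Neither is met.
- Baseline 20%: the 15-point minimum puts the threshold at 20 + 15 = 35%, so a relapse between 5% and 34% is not marrow PD.
- Baseline above 100/1.5 = 66.7%: the increase criterion cannot be met at all.
- The remaining routes to PD are peripheral blasts above 25,000/mcL with a rise of more than 50%, and new extramedullary disease.

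**2. Size of the follow-up bias (illustration).** Assume independent exponential times with medians mP (progression), mD (death) and mS (stop without PD), and hazards p, d and s equal to ln 2 divided by each median. The 90-day visit detects nothing in this first calculation.
- True PFS: S(t) = exp(−(p+d)t), with median 1/(1/mP + 1/mD).
- PFS as written, where progression counts only if it precedes the stop: S(t) = exp(−dt) × [1 − p/(p+s) × (1 − exp(−(p+s)t))].
- Share stopping without PD: s/(p+s+d).

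| mP, mD, mS (months) | Stop without PD | True median | Median as written | Change | True 6-month PFS | 6-month PFS as written |
|---|---|---|---|---|---|---|
| 3, 6, 12 | 14% | 2.00 | 2.09 | +5% | 12.5% | 17% |
| 4, 9, 6 | 32% | 2.77 | 3.19 | +15% | 22% | 32% |
| 6, 9, 3 | 55% | 3.60 | 4.88 | +36% | 31.5% | 45% |

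Check of the last row:
- Share: (1/3)/(1/6 + 1/3 + 1/9) = 0.545.
- At t = 4.88: 2^(−4.88/9) × [1 − (1/3)(1 − 2^(−2.44))] = 0.687 × 0.728 = 0.500.
- At t = 6: 0.630 × 0.708 = 0.446, against a true 2^(−1.667) = 0.315.

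Over the full grid (mP 3, 4, 6; mD 6, 9; mS 3, 6, 12) the median lengthens by about 5-36%. A simulation with 200,000 patients per setting agrees (for example 3.61 to 4.91 months).

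**3. Sensitivity to the 90-day visit and to fast progression.**
- If the visit catches half of the progressions within 3 months of stopping, the range is about 5-31%.
- A second model stops non-responders at week 12. If their median time to progression is 2 months, median PFS is unchanged because about half of the events precede the stop. With no detection at the visit, 6-month PFS is still 32-35% against a true 19-24%.
- In the same model with a median of 3-4 months, 10% of patients staying on drug in marrow CR and 80% detection at the visit, 6-month PFS is about 35-50% against a true 32-48%.

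**The case against.** **Follow-up does not end with the last dose.** A reader might infer that only survival is followed once treatment stops. The calendar contradicts that: the EOT marrow can show marrow PD, and the 90-day examination and differential can show circulating blasts or extramedullary disease. Survival follow-up also asks about MDS/AML (Section 10.3.4), though as a safety report not tied to PFS or DOR. The gap is therefore the lack of a marrow or response assessment at 90 days, and of any disease assessment afterwards.

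**Section 2.3 is not evidence of switching without progression.** A reader might cite its remark on moving to standard therapy. That sentence concerns patients who progress, who already have a PFS event. Section 6.3 alone carries the point, and it names no later therapy.

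**Large effects can be produced.** A reader might infer a median of 5.3-8.9 months against a true 3.6-5.6. That needs a week-12 stop, which 6.3 does not state; removal of everyone outside composite CR, although 6.3 keeps marrow-CR patients on drug; and no detection at 90 days. The documents do not support these as headline figures.

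**The wording could be read kindly.** Last follow-up might mean last follow-up for progression, and progression might include relapse under the cited IWG criteria, whose text is not in the documents. But 9.4.3 uses the same term for OS, and 12.1 separates relapse from PD. An analyst following the text literally would produce the biased result.

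**The endpoints are secondary.** This stands. No hypothesis or go/no-go decision rests on them, and the Simon decisions are untouched.

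**Conclusion.** The concern holds in this form: the rule credits unobserved time as progression-free after a stop without documented progression, and it does not name relapse as an event. The bias in PFS is upward. DOR is biased upward too, for responders who stop without progression and for relapses below the PD thresholds; no size was calculated for DOR.

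The PFS effect is about 5-36% on the median under the assumed grid, none of whose inputs comes from the documents. It is larger if all non-responders stop at a fixed early time and the 90-day visit finds nothing. It is small or absent for the median when progression is fast, and small for 6-month PFS when the visit detects most progressions. The relapse gap rests on the text alone. The change should be made before analysis, but it does not affect the primary endpoint.

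**What to change.** Amend Section 9.4.3 as follows:

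1. Count hematologic relapse, as defined in Section 12.1, as an event for PFS and DOR alongside progression and death.
2. For patients without an event, censor PFS and DOR at the last adequate disease assessment on or before any new anti-leukemic therapy. Let the EOT marrow qualify, and the 90-day examination and CBC if they precede new therapy. Keep last follow-up for OS only.
3. Add a sensitivity analysis for PFS and DOR that counts a stop for non-response, or the start of new therapy, as an event.

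The third item is needed because the censoring in the second is informative: removing non-responders leaves responders over-represented among those at risk. In the week-12 model (median time to progression 3 months in non-responders, 30% CR), censoring at the last assessment gave 6-month PFS of 38-41% against a true 32-33%. If the 90-day visit catches half of the progressions, censoring at the stop was no better than the written rule at 6 months. The sensitivity analysis shows how far the result depends on this.

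The cost is mostly wording. It also brings earlier censoring, some residual upward bias, and one added data item: the start date of new therapy, recorded at existing follow-up contacts, because Section 6.4 does not name it.

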## 12. MEASUREMENT OF EFFECT

### 12.1 Antitumor Effect – Hematologic Tumors

For patients not previously exposed to IDH inhibitors, response is assessed after cycles 1, 3, 6, 9, and 12 for the first year. For patients *with* prior IDH inhibitor exposure, response is assessed after cycles 3, 6, 9, and 12 for the first year on treatment.

Category	Definition	Comment
Complete Response (CR)	Bone marrow blasts <5%; absence of circulating blasts and blasts with Auer rods; absence of extramedullary disease; ANC $\geq 1.0 \times 10^9/L$ (1,000/mcL); platelet count $\geq 100 \times 10^9/L$ (100,000/mcL)*	
CR with incomplete hematologic recovery (CRi)/CRh	All CR criteria except for residual neutropenia ( $<1.0 \times 10^9/L$ [1,000/mcL]) or thrombocytopenia ( $<100 \times 10^9/L$ [100,000/mcL])* CRh: complete remission with partial hematological recovery (platelets > 50,000 mcL and ANC > 500/mcL)	
Morphologic leukemia-free state (“marrow CR”, MLFS)	Bone marrow blasts <5%; absence of blasts with Auer rods; absence of extramedullary disease; no hematologic recovery required	Marrow should not merely be aplastic—at least 200 cells should be enumerated, or cellularity should be at least 10%
Partial response (PR)	All hematologic criteria of CR; decrease of bone marrow blast percentage to between 5% and 25%; and decrease of pretreatment bone marrow blast percentage by at least 50%	Especially important in the context of phase 1-2 clinical trials
Stable disease (SD)	Absence of CR, CRi, PR, MLFS; and criteria for PD not met	The period of stable disease should last at least 3 months

Category	Definition	Comment

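### Section 9.4.3 ends PFS and DOR at progression, death or last follow-up and never names relapse or loss of response, which section 12.1 defines separately and at much lower blast counts

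*Combined protocol and SAP*

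**What the plan says.** Section 9.4.3 ends DOR at the earliest of three times, counting "between the first documentation of response to the time of documentation of progression, death of any cause, or last follow-up, whichever comes first". PFS starts at the first day of therapy and has the same end points. The section does not cite 12.1 and does not mention relapse or loss of response.

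The response table in 12.1 treats the two ideas as separate rows:

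- **PD**, marrow: a more than 50% "increase in marrow blasts over baseline" (with at least a 15-point rise if baseline is below 30%), or a "persistent marrow blast percentage of" more than 70% for at least 3 months. A qualifier on ANC and platelet improvement makes this harder to meet. Other routes are blood blasts rising by more than 50% to above 25 × 10⁹/L, and new extramedullary disease.
- **Relapse**, in the row headed "Hematologic relapse (after CR, CRi"): marrow blasts of 5% or more, or "reappearance of blasts in the blood; or development of extramedullary disease".

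ORR is "calculated as a composite CR+MLFS+PR" (9.4.2), so MLFS and PR are responses. The relapse row covers neither.

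For patients with prior IDH inhibitor exposure, "response is assessed after cycles 3, 6, 9, and 12 for the first year on treatment". Naïve patients have one further assessment after cycle 1. The study calendar has a marrow at end of treatment and none at the 90-day visit. After that visit, 6.4 follows patients for survival about every 3 months.

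**The concern.** PFS and DOR are secondary objectives (1.2.2 and 1.2.4), and DOR bears most directly on the claim in 2.1.1 that olaparib could produce durable remission. If only PD ends these endpoints, a patient who has plainly relapsed stays event-free until the blasts exceed a baseline-referenced threshold or the patient dies. If later PD is never documented, time continues to death or last contact. Both errors lengthen the estimates. If progression was meant to include relapse, the text does not say so, and two analysts could report different medians from the same data.

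**Working it through.** The documents give no sample size, event count or target for PFS or DOR, so there is no stated figure to reproduce. The check compares the 12.1 rules, then asks how far the difference could move a median.

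**1. Gap between marrow relapse and marrow PD (12.1 only).** Relapse starts at 5%. The PD threshold is 1.5 × baseline when baseline is 30% or more, and otherwise the larger of 1.5 × baseline and baseline + 15 points.

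| Baseline blasts | Marrow PD must exceed | Doublings from 5% = log₂(threshold/5) |
|---|---|---|
| 10% | 25% | 2.3 |
| 20% | 35% | 2.8 |
| 30% | 45% | 3.2 |
| 40% | 60% | 3.6 |
| 60% | 90% | 4.2 |
| 67% | 100.5% (unreachable) | – |

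From a baseline of 67% upward, the only marrow route is more than 70% held for at least 3 months. In blood, any reappearance of blasts is relapse, while PD needs more than 25 × 10⁹/L. Extramedullary relapse already meets PD, so it is not lost.

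**2. Responses without a loss rule.** PR requires, among other things, a "decrease of pretreatment bone marrow blast percentage by at least 50" per cent. A patient who goes from 40% to 20% is in PR. By marrow increase, that PR does not end until blasts exceed 60%. Nothing in the printed text says when MLFS or CRh ends.

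**3. Length of the delay.** Scheduled assessments after cycle 3 are 3 × 28 = 84 days apart, or 2.76 months. Relapse at one and PD at the next dates the event 84 days late. As a cross-check with assumed blast doubling times (not in the documents) and baselines of 10% to 60%, the time from 5% to the PD threshold is:

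- 7 days: 16–29 days
- 14 days: 33–58 days
- 28 days: 65–117 days
- 56 days: 130–234 days

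On the 84-day schedule that is one to three assessments.

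**4. Effect on median DOR (assumption-based).** Assume exponential DOR with a true median of 6.0 months, so L = ln 2/6 = 0.1155 per month. A share q of DOR events is dated d months late. The reported median M solves (1 − q)e^(−LM) + q·e^(−L(M − d)) = 0.5, which for M > d gives M = 6 + ln(1 − q + q·e^(Ld))/L.

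Worked case: for d = 2.76, e^(Ld) = 1.376. With q = 0.5, M = 6 + ln(1.188)/0.1155 = 7.49.

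| Delay d | q = 0.25 | q = 0.50 | q = 1.00 |
|---|---|---|---|
| 1 month | 6.26 | 6.51 | 7.00 |
| 2.76 months (84 days) | 6.78 | 7.49 | 8.76 |

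**5. Last follow-up.** Each survival contact after the 90-day visit can add about 3 months with no scheduled disease assessment, so four contacts add 12 months. This applies only to patients who stop treatment without a documented event, and the documents do not size that group.

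**The case against.** The strongest reply is that progression is used loosely and was probably meant to include relapse. Section 9.4.3 does not cite the 12.1 table. Section 6.3 lists disease progression and clinical progression separately, and the correlative sections speak of progression samples in one place and relapse time points in another. Sections 9.1.2.1 and 9.6.2 name the AML IWG 2003 and MDS IWG 2006 criteria, which may contain rules that the printed table lacks. This supports calling the text ambiguous. It does not remove the problem, because the protocol's own table separates the two terms and nothing joins them.

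Several points on size do stand:

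- The 6.0-month median, the values of q and the 1-month delay are assumptions. The model also treats q as a share of all DOR events, so deaths in remission must count among the undelayed ones.
- Blood counts and examinations every cycle, an end-of-treatment marrow, or death can date an event sooner than 84 days. The 90-day visit has a blood count and examination, though no marrow.
- In the IDH-inhibitor-naïve arms (78 of the 104 tabulated patients), 6.3 ends treatment in the absence of CR/CRh/mCR. This limits the PR example there.
- Median PFS may move little, because only responders are affected and the design CR rates run from 5% to 50%.
- At the 35% alternative, the exposed arms would yield about 5 (14 × 0.35) and 4 (12 × 0.35) complete responders, so most of the modelled shifts are small against sampling error.

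**Conclusion.** The concern holds. Followed as written, 9.4.3 dates sub-threshold marrow and blood relapses late or misses them, gives no end rule for MLFS, PR and CRh, and can credit survival contacts as progression-free time. The direction, longer DOR and longer PFS in responders, follows from the definitions alone. The size does not: under the stated assumptions, a true median DOR of 6.0 months would read 6.3 to 8.8 months, and no PFS figure can be given. If analysts already count relapse as progression, that part of the bias disappears, but the text still needs to say so. These are secondary estimates. The composite CR endpoint and the Simon decision rules do not depend on this point.

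**What to change.** In 9.4.3, define the PFS and DOR event as the earliest of progressive disease, hematologic relapse or loss of response by the applicable criteria, and death. State which criterion applies after each of CR, CRi, CRh, MLFS and PR. Censor patients without an event at the last disease assessment, replacing last follow-up. For the MDS arms, reconcile the 12.1 table with the MDS IWG 2006 criteria named in 9.1.2.1 and say which set defines progression and relapse. A sensitivity analysis censoring at new anti-leukemic therapy would be a useful addition.

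The cost is wording in 9.4.3 and one reconciling statement, with no new visits. The sensitivity analysis needs the start date of new therapy. The documents do not show that it is captured, so one CRF field may be needed. Reported medians may be shorter than under the literal text. Censoring at the last assessment can itself be informative if patients leave because they are declining, which the report should acknowledge.
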